8. Provide ongoing consultation	
Definition: provide implementers with continued consultation with regards to OEND best practices.
 
Actor: external implementation advisor (see above).
 
Action: web-based meetings with direct interaction between external implementation advisor and SSP staff.
 
Action Target: SSP staff, including OEND implementation team and leadership
 
Temporality: begins within 1 month of enrolling into the trial, occurs via web-based meetings up to monthly for twelve months and as needed via electronic communication

SSP staff and organizational leadership in the OMIE arm were provided the opportunity to participate in 60-minute sessions once a month for up to 12 months. In addition to monthly sessions, facilitators were provided up to 2 hours to prepare for sessions and to identify and distribute resources to SSPs based on identified priorities. All sessions were offered virtually over audio-visual connections. Thus, the maximum possible dose for each SSP was 12 sessions or 36 hours. To maximize the extent to which the approach was implemented with consistency and quality, the project's lead and the study coordinator trained each facilitator, reviewed randomly selected facilitation session recordings, and held group supervisory meetings weekly to discuss successes, lessons learned, and emerging issues.

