#### Data Collection

We carried out an interview-administered survey at SSPs baseline visit and at their 12-month follow-up after all facilitation-based activities had occurred. SSPs were paid a \$50 incentive for their time (~30 minutes) completing the baseline and the 12-month follow-up survey. In addition, the study coordinator tracked the number of sessions and the number of hours between external facilitators and SSP teams as part of a log of implementation activities. Follow-up to complete the 12-month follow-up survey ended in February 2022, marking the end of the trial approximately 12 months after the last SSP was enrolled.

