#### Masking

Masking the SSP organizations and their staff to the assigned implementation strategy condition was not possible. Aside from the external facilitators who delivered the implementation strategies, research staff were blinded to all condition assignments, including the statistician throughout all analyses.

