#### Statistical Analysis Plan

Statistical analyses were conducted using an intent-to-treat approach. Descriptive statistics were used to summarize continuous outcomes and covariates by experimental condition; frequencies and percentages were used to summarize categorical measures. Given the varying sizes of SSPs, counts of naloxone doses and individuals receiving naloxone were summarized as a rate per number of participant contacts for syringe services in the past 3 months.

Negative binomial regression models were used to compare the number of naloxone doses distributed and contacts for naloxone refills or trainings by condition; the number of contacts for syringe services in the past 3 months was included as an offset. The model for naloxone doses was adjusted for baseline rate given the difference between conditions at baseline. The mean number of best practices adopted were compared by condition using a two-sample t-test. We also carried out a per-protocol dose response analyses, where OMIE SSPs were dichotomized at the median for the number of OMIE sessions (<10 sessions; 10+ sessions) and number of OMIE hours received (<12 hours; 12+ hours) and compared to Control SSPs. P-values <0.05 were considered statistically significant a priori. All analyses were conducted using Stata 16.1 (StataCorp LLC, Texas USA).

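### The dose-response analysis compares OMIE SSPs grouped by attendance after randomisation with all Control SSPs, so a gradient cannot be read as an effect of more OMIE; its hours measure and its fit with the masking statement also need reconciling

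*Combined protocol and SAP*

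**What the plan says.** The Statistical Analysis Plan makes intent-to-treat the main approach. It then adds an analysis that it calls a per-protocol dose response: "OMIE SSPs were dichotomized at the median for the number of OMIE sessions (<10 sessions; 10+ sessions", and likewise by "number of OMIE hours received (<12 hours; 12+ hours". The resulting groups are compared with Control SSPs. Significance is set at p<0.05. Adjustment for baseline is stated only for the naloxone-dose model; best practices are compared by a two-sample t-test. The dose-response analysis carries no exploratory or non-causal label.

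The text after Table 1 says that OMIE SSPs "were provided the opportunity to participate in 60-minute sessions once a month for up to 12 months", and that "the maximum possible dose for each SSP was 12 sessions or 36 hours". Strategy 8 in Table 1 adds consultation that "occurs via web-based meetings up to monthly for twelve months and as needed via electronic communication". Under Data Collection, "the study coordinator tracked the number of sessions and the number of hours between external facilitators and SSP teams".

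Masking states: "Aside from the external facilitators who delivered the implementation strategies, research staff were blinded to all condition assignments, including the statistician throughout all analyses". The text after Table 1 says that the project's "lead and the study coordinator trained each facilitator, reviewed randomly selected facilitation session recordings".

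**The concern.** The number of sessions an SSP takes up is settled after randomisation and depends partly on the SSP. Control SSPs have no attendance, so no matching Control subgroup can be formed. Each contrast therefore sets a selected part of one arm against the whole of the other. If SSPs that attend more would have had different outcomes anyway, selection alone could create, hide or reverse a gradient. A reader could then take a selection effect as evidence that more facilitation works better, or worse.

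Two related points affect what the analysis means and who could have run it. The hours cut does not sit easily with the session cut or with the two descriptions of hours elsewhere. Forming the groups also uses data that only one arm can have, while the masking statement covers all analyses and exempts only the facilitators.

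**Working it through.** **The plan's own figures.** The plan gives no figure for the dose-response analysis itself. Two related figures reproduce and are not disputed.
- Maximum dose: 12 × (1 h session + 2 h preparation) = 36 h.
- Sample size: the SD of the mean of two measurements correlated 0.3 is √((1 + 0.3)/2) = 0.806. At d = 0.45 and two-sided 5% this needs 51 per arm, and 50 per arm gives 79.7% power against the stated 50 and 80%.

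**Size of a selection effect (illustration, best practices).** Inputs:
- 105 SSPs (Study Objective). Arm sizes are not given, so 52 per arm is assumed.
- An even split of the OMIE arm, 26 and 26, and an outcome SD of 1.
- No true OMIE effect.
- A correlation r between attendance and the outcome the SSP would have had anyway. The documents give no value, so a range is shown.

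The mean of the upper half of a standard normal is φ(0)/0.5 = 0.798. The expected shift against Control is therefore 0.798 × r for high attenders and −0.798 × r for low attenders. The standard error is √(1/26 + 1/52) = 0.240. Rejection rates come from the noncentral t with 76 df and noncentrality shift/0.240.

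| r | Shift (SD) | Two-sided rejections, each contrast |
|---|---|---|
| 0 | 0 | 5% |
| 0.1 | 0.08 | 6% |
| 0.2 | 0.16 | 10% |
| 0.3 | 0.24 | 17% |
| 0.5 | 0.40 | 37% |

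A negative r reverses the signs. A simulation with 50 per arm agrees within a percentage point, and in it the randomised comparison stays near 5% throughout.

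Sessions are whole numbers and ties at 10 fall in the upper group, so the split may be uneven. With 60% at 10 or more (31 and 21) and r = 0.3, the shifts are 0.644 × 0.3 = 0.19 SD and −0.966 × 0.3 = −0.29 SD. Rejections are about 13.5% and 19.7%. No figures are given for the two naloxone count outcomes.

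**What baseline adjustment does.** Let ρ be the correlation between baseline and follow-up, and b the correlation between attendance and the baseline outcome. The shift left after adjustment is about 0.798 × (r − ρb). At r = 0.3:
- b = 0.3, ρ = 0.3 (Targeted Sample Size): 0.798 × 0.21 = 0.17 SD.
- b = 0.3, ρ = 0.7 (assumed): 0.798 × 0.09 = 0.07 SD.
- b = 0: 0.24 SD, unreduced.

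**What a baseline table can show.** With b = 0.3, the expected high-minus-low gap at baseline is about 0.47 SD, with standard error √(2/26) = 0.28. It reaches p<0.05 only about 40% of the time.

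**Hours.** Ten 60-minute sessions give 10 h, and the maximum of twelve gives 12 h. Both cuts are said to be medians, yet the session cut is 10 and the hours cut is 12. The 36-hour maximum includes preparation. Data Collection describes time between facilitators and SSP teams, which on its plain wording does not. Sessions that ran over, or electronic consultation, could account for the gap; the text does not say.

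**Masking.** Finding the OMIE median, splitting on it and naming Control as comparator all use data that exist only for OMIE SSPs. No coded dataset, separate unblinded analyst or unblinding step is described. Separately, the coordinator kept the session log and, with the project lead, trained facilitators and reviewed recordings, yet only facilitators are exempted.

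**The case against.** The plan already sets this analysis apart. Intent-to-treat comes first, the dose analysis is an addition with its own label, and the documents draw no dose-effect conclusion. That stands, and it limits the harm to over-reading a supplementary result. It does not remove it: the analysis is named a dose response, shares the p<0.05 rule and has no caveat.

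A reader might infer that the analysis could not be run blind at all. The documents do not support that. Someone holding the log could have passed the statistician a coded three-level variable. Group sizes (about half the sample against two quarters), and the one group unchanged between the session and hours splits, would probably reveal Control, but that is not impossibility. What stands is that no such step is described. The issue of the coordinator and project lead does not depend on the dose analysis, but it concerns the same masking statement.

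A reader might also infer that hours are undefined, or that preparation was counted. Data Collection does describe the logged hours, as contact time on a plain reading. The supportable point is that the passages do not clearly describe one measure.

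Finally, the figures rest on an assumed r, and at 0.1 the test is close to nominal. That is fair, which is why a range including zero is shown. Nor can adjustment be presumed to help: it does so only to the extent that attendance is related to the baseline outcome.

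**Conclusion.** The concern holds in this limited form. Neither dose-group contrast is protected by randomisation; this follows from the design and needs no assumption about why SSPs attended. How much it matters cannot be determined from the documents. The spurious shift ranges from none at r = 0 to about 0.40 SD at r = 0.5, close to the design effect of 0.45, under the assumptions listed in the working. The direction is unknown, so it should not be presumed that high attenders would look better.

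The documents do not support reading this as a flaw in the intent-to-treat comparison, which the selection does not touch. Nor do they show that the primary analyses were unblinded: these could have been finished on coded arms before the session log was merged, but the plan does not say. The masking statement as worded is hard to reconcile with the dose analysis and with the roles of the coordinator and project lead, and the measure of hours needs clarifying.

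**What to change.** 1. Adjust every dose-group comparison for the baseline value of the outcome where it was collected, as is already stated for naloxone doses. Follow-up ended in February 2022, so label any further variables from the Covariates section as post hoc. Say that adjustment lowers bias only to the extent that attendance is related to baseline.
2. Tabulate baseline outcomes and covariates for Control, low-attendance and high-attendance SSPs. Note that lack of imbalance does not exclude selection, and that with about 26 per group an apparent gradient may be chance.
3. Report the analysis as exploratory and non-randomised, with no dose-effect conclusion.
4. Reconcile the OMIE section, Data Collection and the Statistical Analysis Plan on what the hours count: session time, preparation or electronic consultation.
5. Reconcile Masking with those sections. Limit the statement to the staff and analyses actually blinded, and state whether the primary analyses were finished before the session log was merged.

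Cost: one extra table, a little more analysis of data already held, and changes of wording. The downside is a weaker claim from the dose analysis.

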### Recruitment, Eligibility, and Enrollment

To be eligible, an organization must have: 1) met the definition of an SSP – a program which primary function is to engage people who use drugs and provide them free drug use supplies to reduce harms associated with drug use, 2) implemented OEND for a minimum of 6 months, and 3) completed the NSSSP fielded from February to July 2019. We excluded organizations such as fire departments or emergency departments of hospitals that offered drug use supply distribution since it would be an ancillary function of these organizations and OEND programs that were not part of a SSP.

A total of 243 SSPs participated in the survey and were determined to be eligible. SSPs were organized into a randomized list and were contacted sequentially for recruitment into the trial. We recruited SSPs from September 2019 to February 2021. Within that timeframe, we paused recruitment activities from March to July 2020 due to the onset of the COVID-19 pandemic. The pause in recruitment activities primarily provided an opportunity for SSPs to adapt to COVID-19 changes, particularly for their adjustment to stay-at-home orders and adoption of delivery models that minimized close person-to-person contact.

To recruit SSPs, our study team initially contacted people in leadership role(s) at each SSP via email to set up a call to explain the study and carry out enrollment activities for organizations that were interested. Organizational leadership included executive directors, program managers, and/or site coordinators. For organizations interested in participating in the trial, study staff would obtain electronic/written informed consent from the organization to join the study, carry out the organizational agreement for participation, and administer the baseline survey. Following the baseline survey, SSPs were randomized using simple randomization to two study arms: 1) dissemination of OEND best practice recommendations (i.e., Control SSPs), or 2) the Organize and Mobilize for Implementation Effectiveness (OMIE) approach along with dissemination of the OEND best practice recommendations (i.e., OMIE SSPs). Sequentially numbered sealed envelopes were used to implement the random allocation sequence, which were concealed until the point of randomization.

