#### Targeted Sample Size

The targeted sample size was estimated using PASS software [49]. We estimated that a sample of 100 SSPs (50 per arm) would provide 80% statistical power to detect a statistically significant ( $p<0.05$ ) medium effect size (Cohen's  $d = 0.45$ )[50] between study arms, assuming an

alpha of 0.05, standard deviation of 1.0 and two repeated measurements (baseline and 12-month follow-up) with a first-order autoregressive covariance structure and a correlation between observations on the same SSP of 0.3.

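### The dose-response analysis compares each half of the OMIE arm only with Control, so as written it tests no gradient and cannot support a dose-response statement.

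*Combined protocol and SAP*

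**What the plan says.** The last paragraph of the Statistical Analysis Plan section adds a per-protocol analysis that it calls dose response. OMIE SSPs are "dichotomized at the median for the number of OMIE sessions (<10 sessions; 10+ sessions" in one version. The other uses the "number of OMIE hours received (<12 hours; 12+ hours) and compared to Control SSPs". The same paragraph gives the decision rule for all tests: "P-values <0.05 were considered statistically significant a priori".

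The section names no high-versus-low contrast, no trend test and no model with sessions or hours as a continuous term. It does not say what pattern of results would count as dose response. The Targeted Sample Size section plans only for the two whole arms: a "sample of 100 SSPs (50 per arm) would provide 80% statistical power".

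**The concern.** A dose-response statement says that outcomes differ between SSPs that received more OMIE and SSPs that received less. Neither planned contrast makes that comparison. Each asks whether one half of the OMIE arm differs from Control.

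With only a p-value threshold for guidance, the natural reading of the output is to see which half crosses it. A significant result beside a non-significant one is not evidence that the two differ. With about 26 SSPs in each half, such split results are common when the effect is the same in both. The report could then suggest that OMIE works only from 10 sessions upward when there is no gradient.

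This is separate from attendance being chosen after randomisation. The gap would remain even if the number of sessions had been assigned at random.

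**Working it through.** **1. The plan's own figure.** Inputs from Targeted Sample Size: 50 SSPs per arm, d = 0.45, "alpha of 0.05, standard deviation of 1.0 and two repeated measurements (baseline and 12-month follow-up", and "a correlation between observations on the same SSP of 0.3". Sidedness is not stated; I use two-sided.

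- Effective SD of the average of two measurements: √((1 + 0.3)/2) = 0.806.
- Standard error of the difference: 0.806 × √(2/50) = 0.161.
- Power: Φ(0.45/0.161 − 1.96) = Φ(0.83) = 79.7%.

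This reproduces the stated 80%, which applies to 50 versus 50 and not to half an arm.

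**2. Assumed group sizes.** The Study Objective section gives 105 SSPs in total; the document gives no sizes by arm or by half. I assume 52 Control and 53 OMIE, split 26 low and 27 high, and vary this below. The outcome is normal with SD 1.0 at follow-up, which matches the two-sample t-test planned for best practices.

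**3. The two contrasts under a flat effect d.**

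- Standard errors: low versus Control √(1/52 + 1/26) = 0.240; high versus Control √(1/52 + 1/27) = 0.237.
- Correlation through the shared Control arm: (1/52)/(0.240 × 0.237) = 0.34.
- At d = 0.45, power is about 46% (low) and 47% (high).

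Simulation (1,000,000 draws per row, pooled t-tests, two-sided 0.05) gives the chance that the high half is significant in OMIE's favour and the low half is not:

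| Flat effect d | High only | Direct test finds high > low |
|---|---|---|
| 0 | 2% | 2.5% |
| 0.2 | 9% | 2.5% |
| 0.3 | 15% | 2.5% |
| 0.45 | 20% | 2.5% |
| 0.6 | 17% | 2.5% |
| 0.8 | 7% | 2.5% |

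At d = 0.45 the full split is: both significant 27%, high only 20%, low only 19%, neither 35% (rounded). When the high-only pattern occurs, a direct high-versus-low test is significant in only 11% of cases.

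**4. Sensitivity at d = 0.45.**

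- Uneven halves: 31 low and 22 high gives 15%; 18 low and 35 high gives 28%.
- With the SD of 0.806 from step 1, the near-even split gives 19%.

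**5. What a direct contrast could detect.** The standard error of high minus low is √(1/26 + 1/27) = 0.275. For 80% power the difference between halves must be (1.96 + 0.84) × 0.275 = 0.77 SD, or 0.77 × 0.806 = 0.62 on the smaller SD.

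**The case against.** The strongest objection is that the plan never says dose response will be read from which half is significant. Comparison with Control could equally mean a three-level group in one model, with ordered estimates and confidence intervals. That stands: the significance-pattern rule is an inference. What the text does support is that no gradient test and no rule of interpretation are stated. Ordered estimates judged by eye would not be a test either.

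Second, a reader might infer that any flat effect will look like dose response in one trial in five. The figures do not support that. The planning effect lies near the peak of the curve, and the rate falls on both sides of it. The size of the halves also matters. Sessions are capped at 12 and the cut is at 10, so ties at the median are likely and the halves may be far from equal.

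Third, a reader might compound the rate over the three outcomes as if they were independent. Doses distributed and participants receiving naloxone cover the same 3 months and are closely linked, and the document gives no correlations, so I give no combined figure. Those two outcomes are also analysed by negative binomial regression, for which normal-outcome figures are only a proxy.

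Finally, this is an additional analysis and leaves the main comparison by arm untouched. Nothing in the document says that session numbers will be set from it. Both points are right and limit the weight of the concern, but they do not remove the gap.

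**Conclusion.** The point holds in a bounded form. As written, the analysis carries a dose-response label but contains no comparison between levels of dose, so it cannot support a dose-response statement for either sessions or hours. This follows from the text and depends on no distributional assumption.

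The size of the possible error is conditional. It requires that dose response be read from one half being significant and the other not. Under that reading, about one in five is the rate for one outcome and one dose measure, with a normal outcome, near-even halves and a flat effect equal to the planning value. The ranges in the working should be stated with it. The point warrants a change to a secondary analysis; it does not cast doubt on the primary results.

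**What to change.** For each outcome and each dose measure, fit Control, low and high as three groups in one model of the same family as the main analysis. For the two naloxone outcomes that is negative binomial with the same offset, and with baseline adjustment where the main model has it. For best practices it is a linear model. Report the high-minus-low contrast (a rate ratio in the count models) with its 95% CI, and the number of SSPs in each half. A slope on sessions or hours within the OMIE arm may be added as supportive.

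State that no dose-response claim is made unless the interval for the direct contrast excludes no difference. Present the contrasts of each half with Control as descriptive. Label any gradient an exploratory association, because attendance arose after randomisation and the direct contrast does not remove that selection.

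The cost is a few sentences and one refitted model per outcome and dose measure. The Data Collection section says that sessions and hours were already logged, so no new data are needed. The downside is low power: with about 53 OMIE SSPs only a difference of roughly 0.6 to 0.8 SD between halves would be detected reliably, so the usual answer will be no evidence of a gradient. Since the plan is written in the past tense and cuts at the median, a contrast added now should be described as post hoc if results are already known.

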#### Trial Outcomes

Our primary outcomes center on the multidimensional variable of implementation effectiveness (i.e., the consistency and quality of OEND implementation by SSP staff). Implementation effectiveness fit our broad objectives, by focusing on the extent to which our multifaceted, facilitation-based approach impacted OEND delivery at the organizational level. Accordingly, SSPs represent the primary unit of analysis. Proctor et al.'s taxonomy of implementation outcomes informs our operationalization of implementation effectiveness, focusing on the reach of SSPs' naloxone distribution (i.e., consistency) and fidelity to OEND best practices (i.e., quality)[46]. As such, the primary outcomes were the number of naloxone doses distributed in the past 3 months; the number of SSP participants receiving naloxone in the past 3 months, and the number of OEND best practices implemented. Importantly, prior research has shown that larger scale naloxone distribution has led to reductions in opioid overdose mortality, further supporting use of these measures as trial outcomes [17, 47, 48].

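### The dose-group comparisons with Control have an unadjusted 0.05 rule and no hierarchy or exploratory label, so a chance result can be claimed as an effect; limiting the claim is a cheap improvement

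*Combined protocol and SAP*

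**What the plan says.** The section Trial Outcomes names three primary outcomes. Two are given as follows: "the primary outcomes were the number of naloxone doses distributed in the past 3 months; the number of SSP participants receiving naloxone". The third is best-practice fidelity: "and the number of OEND best practices implemented". The Statistical Analysis Plan first sets out an intent-to-treat comparison of the arms for these outcomes. It then adds a per-protocol dose-response analysis in which the OMIE SSPs are "dichotomized at the median for the number of OMIE sessions (<10 sessions; 10+ sessions) and number of OMIE hours received (<12 hours; 12+ hours". Each group is set against the Control SSPs.

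The next sentence is the section's only decision rule: "P-values <0.05 were considered statistically significant a priori". Nothing limits that rule to the intent-to-treat tests. The section gives no adjustment, no testing order and no lead exposure measure, and it does not call the dose analysis exploratory or secondary. It also does not say which outcomes enter the dose analysis, or whether the groups are tested one by one or through a single overall test.

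**The concern.** The same OMIE SSPs are split twice, by two closely related measures of exposure, and each half can be set against the same Control arm. For any one outcome, OMIE therefore gets up to four more chances at p<0.05 after its intent-to-treat test.

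What is at stake is a neutral intent-to-treat result followed by a statement that OMIE worked at some level of exposure, resting on one half of one split. Chance alone can produce this, even when attendance has nothing to do with outcome. It adds to any bias from the fact that SSPs select themselves into the dose groups after randomisation. It is also separate from the question of three unadjusted primary tests, because it already arises within a single outcome.

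**Working it through.** **The plan's own figure.** Targeted Sample Size states that "a sample of 100 SSPs (50 per arm) would provide 80% statistical power" at d = 0.45. Its stated inputs are "alpha of 0.05, standard deviation of 1.0 and two repeated measurements (baseline and 12-month follow-up) with a first-order autoregressive covariance structure". The within-SSP correlation is taken as 0.3. The mean of two measurements has SD √((1+0.3)/2) = 0.806. Then 0.45/(0.806 × √(2/50)) = 2.79, and power = Φ(2.79 − 1.96) = 79.7%. The stated 80% is reproduced with a two-sided 0.05 test. Sidedness is not stated, so two-sided is assumed below. This calculation covers the comparison of arms only, not the dose groups.

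**Number of tests.** 2 measures × 2 groups = 4 per outcome; × 3 outcomes = 12. Twelve is a maximum, because the plan does not define the set.

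**Reference bounds if tests were independent.** 1 − 0.95⁴ = 18.5% for one outcome; 1 − 0.95¹² = 46.0% for three. Both are too high, because the tests share the Control arm and the two splits overlap. With 50 Control SSPs and halves of 25, the two halves of one split give test statistics with correlation (1/50)/(1/50 + 1/25) = 0.33.

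**Simulation under no effect.** The inputs below are assumptions, since the documents do not give them:
- 52 Control and 53 OMIE SSPs (105 SSPs are documented; the split is assumed).
- Normal outcomes, with correlation 0, 0.5 or 0.9 between them.
- Attendance unrelated to outcome.
- Latent correlation between sessions and hours of 0.7 or 0.95. By ½ + arcsin(r)/π, the two splits then agree for about 75% or 90% of SSPs.
- Even median splits and pooled two-sided t-tests at 0.05.

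With 20,000 null trials per setting, the Monte Carlo standard error near 30% is √(0.3 × 0.7/20,000) = 0.3 points. Each cell gives the result for sessions-hours correlation 0.7 / 0.95.

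| Event | Outcome corr. 0 | 0.5 | 0.9 |
|---|---|---|---|
| Any of 12 dose tests significant, either direction | 36% / 33% | 32% / 28% | 22% / 20% |
| Any of 12 favours OMIE, no intent-to-treat primary test significant | 12% / 10% | 10% / 9% | 7% / 6% |
| Any of 12 significant after gating on the same outcome's intent-to-treat test | 13% / 13% | 12% / 11% | 8% / 8% |

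For a single outcome, the correlation between outcomes plays no part:
- Any of 4 dose tests significant: 12-14%.
- A dose group favouring OMIE while that outcome's intent-to-treat test is not significant: 4-5%.
- Any of 4 significant after gating: 4-5%.

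**Second check.** A separate calculation used z-tests, 50 SSPs per arm and 25/25 halves. With 80-90% agreement between splits, any of 12 is 29-31% at outcome correlation 0.5. Letting agreement run from 50% to 100% and outcome correlation from 0 to 0.9 widens the range to 16-37%.

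**The case against.** The strongest reply is that the dose analysis is visibly subordinate. It comes after the intent-to-treat models, is introduced as an addition, carries a per-protocol label, and has no part in the sample-size calculation. That has some force, and the significance sentence does not say in terms that it covers the dose tests. But it follows them directly and without restriction, so a reader applying the plan as written would call any dose-group p<0.05 statistically significant.

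A second reply is that the size depends on assumptions, and this stands. The outcome correlation and the overlap of the two splits are assumed. The two count outcomes are to be analysed with negative binomial models, not normal tests, and the distribution of sessions is not given. The single-outcome figure of 12-14% does not depend on the outcome correlation, but it keeps the other assumptions.

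Some stronger readings are tempting and should be resisted:
- A reader might infer that an ineffective OMIE has a 30% chance of a false claim that it works. The 30% counts both directions, includes trials where an intent-to-treat test is itself falsely significant, and needs all three outcomes tested group by group. The figure that matches the harm is 9-10%.
- A reader might infer that sessions should be the main measure. The description of OMIE gives the maximum dose both as 12 sessions and as 36 hours, so the documents offer no basis for preferring either.
- A reader might infer that a gate added now restores pre-specified error control. The plan is written in the past tense, follow-up ended in February 2022, and the median cut-points are already numbers.

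**Conclusion.** The point holds as a cheap improvement. As written, the plan lets up to four overlapping dose-group tests per outcome be called significant at 0.05, whatever the intent-to-treat test shows. If OMIE had no effect, and under the stated assumptions, some dose-group test would be significant in about 12-14% of trials for one outcome. Across three outcomes the figure is about 20-36%, or about 30% at outcome correlation 0.5. The misleading case, a dose group favouring OMIE with no significant intent-to-treat primary test, has a chance of about 9-10% across three outcomes (range 6-12%). For one outcome, against its own intent-to-treat test, it is about 4-5%. These are chance-only figures; selection by attendance is a separate problem that they do not measure. The intent-to-treat analyses are not affected.

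**What to change.** In the Statistical Analysis Plan, state that a dose-group comparison supports a claim of statistical significance only if the intent-to-treat test for the same outcome has p<0.05. Otherwise report both the sessions split and the hours split as estimates with 95% CIs, labelled exploratory and non-randomised, with no significance claim. State also which outcomes enter the analysis and whether the groups are tested one by one.

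Under no effect, every dose claim then needs an intent-to-treat rejection first, so the per-outcome rate is at most 5%. Across three outcomes about 11-12% remains at outcome correlation 0.5; that remainder belongs to the separate question of three unadjusted primary tests. Gating does not remove selection by attendance, which is why the non-randomised label is needed.

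If the rule is added after the data have been seen, report it as a limit on what is claimed, not as pre-specified error control. The cost is a few sentences and no new data. The downside is that an effect confined to high-attending SSPs could be reported only as exploratory when the intent-to-treat test misses.
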